14.6.3.2 GCAS

The GCAS is assessed (when applicable) at Baseline, Weeks 2, 4, 8, 12, 16, 28, 40 and Week 52/ET visits.

The overall post-OL Baseline worst suicidality rating will be summarized using the number and percentage of subjects within each rating. The number and percentage of subjects

reporting any post-OL Baseline rating of 3 or 4 will be tabulated. For calculating percentages, the denominator is the number of subjects with an OL GCAS assessment at the given visit and within each cohort. The above summaries will be presented only for the OL study period and using the clinician ratings.

Subject and study partner/caregiver ratings will not be summarized but will be included in data listings.

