3.5 Determination of Sample Size

Up to approximately 750 subjects will be enrolled. The sample size for this study is not based on statistical power, but will depend on the number of subjects who transition into this OL extension study from the antecedent study.

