5.1 General Data Reporting Conventions

For continuous variables, the following summary statistics will be provided: number of subjects, mean, standard error of the mean (SE), standard deviation (SD), minimum,

maximum, and median. Unless specified otherwise, means, medians, and confidence intervals will be presented to one more decimal place than the raw data, and the SDs and SEs will be presented to 2 more decimal places than the raw data.

For categorical variables, summaries will include the number and percentage of subjects in each category, using the number of subjects with non-missing values as the denominator for the percentages (unless otherwise specified). Categories with zero counts will not have zero percentages displayed. Percentages will be presented to 1 decimal place.

When converting number of days to months, it will be calculated as the number of days divided by 365.25 and then multiplied by 12. When converting number of days to years, it will be calculated as the number of days divided by 365.25.

All endpoints will be summarized using the Safety Analysis Set.

No hypothesis testing is planned. Descriptive summaries of all safety and efficacy endpoints will be provided.

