5.3.4 C-SSRS

The C-SSRS is assessed (when applicable) at Baseline, Weeks 2, 4, 8, 12, 16, 28, 40 and Week 52/ET visits.

The Columbia-Suicide Severity Rating Scale (C-SSRS) will be used to assess suicidal ideations and behaviors in subjects who are able to complete the assessment (subjects without dementia, defined as an $MMSE \geq 25$), and subjects with dementia who the Investigator has determined can complete the C-SSRS. The C-SSRS monitors changes in suicidal thinking and behavior over time, in order to determine risk. Four constructs are measured: the severity of ideation, the intensity of ideation, behavior, and lethality.

The C-SSRS version assessing information since the last visit will be completed at all visits (including the Baseline visit). The C-SSRS results for each subject should be reviewed by the Investigator at each visit. If at any time the C-SSRS results for a given subject reveal potential suicidality, then the Investigator should assess the clinical significance of such results. If a clinically significant risk of suicidality is identified for a subject, then the Investigator should discontinue the subject and implement appropriate treatment.

There are 5 questions about suicidal ideation, representing 5 types of suicidal ideation: wish to be dead; non-specific active suicidal thoughts; active suicidal ideation with any methods (not plan) without intent to act; active suicidal ideation with some intent to act, without specific plan; active suicidal ideation with specific plan and intent. If a subject answers “yes” to any of these 5 questions, this subject will be counted as having suicidal ideation.

There are 5 questions about suicidal behavior, representing 5 types of suicidal behavior: preparatory acts or behavior; aborted attempt; interrupted attempt; actual attempt; suicide. If a subject answers “yes” to any of these 5 questions, this subject will be counted as having suicidal behavior.

Missing C-SSRS item scores will not be imputed.

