5.3.5 GCAS

The GCAS (when applicable) is assessed at Baseline, Weeks 2, 4, 8, 12, 16, 28, 40 and Week 52/ET visits.

If the subject is not able, in the Investigator's judgement, to reliably complete the C-SSRS the Global Clinical Assessment of Suicidality (GCAS) will be administered and used thereafter in the study. If the GCAS was used in the antecedent study, suicidality since last visit will be assessed at Baseline and at all other visits. The first assessment with the GCAS should assess lifetime suicidality and suicidality for the past 3 months, and at all other visits suicidality since the previous visit will be assessed.

The GCAS is a clinician-rated, 5-point scale that is designed to rate the subject's suicidality based on the report of the subject, the report of the study partner/caregiver, and the clinician's global assessment. Ratings are scored as follows: 0=absent; 1=feels life is not worth living; 2=wishes he/she were dead or any thoughts of possible death to self; 3=suicidal ideas or gesture; 4=attempt at suicide. The Investigator will record a subject rating, a study partner/caregiver rating, and a clinician rating.

Missing scores will not be imputed.

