14.6.3.1 C-SSRS

The C-SSRS is assessed (when applicable) at Baseline, Weeks 2, 4, 8, 12, 16, 28, 40 and Week 52/ET visits.

The event counts and the number and percentage of subjects reporting any post-OL Baseline suicidal ideation (wish to be dead; non-specific active suicidal thoughts; active suicidal ideation with any methods (not plan) without intent to act; active suicidal ideation with some intent to act, without specific plan; active suicidal ideation with specific plan and intent), suicidal behavior (preparatory acts or behavior; aborted attempt; interrupted attempt; actual attempt; suicide), or suicidality (any suicidal ideation or behavior) will be tabulated.

The event counts and the number and percentage of subjects reporting any post-OL Baseline non-suicidal self-injurious behavior will also be tabulated.

For calculating the percentages, the denominator will be the number of subjects with an OL C-SSRS assessment within each cohort. The above summaries will be presented only for the OL study period.

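### Suicidality is tabulated scale by scale, so no planned table counts each subject once across the C-SSRS and GCAS or separates C-SSRS ideation already present at open-label Baseline (minor)

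*SAP*

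**What the plan says.** Suicidality is the first safety item under the exploratory objectives (Protocol 2.2; SAP 2.3). It is measured with the C-SSRS in subjects who can complete it reliably, and otherwise with the GCAS. Once a subject goes over to the GCAS, that scale is kept (SAP 14.6.3).

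**C-SSRS.** SAP 5.3.4 describes five ideation questions, "representing 5 types of suicidal ideation: wish to be dead; non-specific active suicidal thoughts" being the first two. On a yes to any of the five, "this subject will be counted as having suicidal ideation". SAP 14.6.3.1 tabulates post-Baseline ideation, behavior and their union, and "the denominator will be the number of subjects with an OL C-SSRS assessment within each cohort".

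**GCAS.** SAP 5.3.5 gives the ratings: "2=wishes he/she were dead or any thoughts of possible death to self; 3=suicidal ideas or gesture; 4=attempt at suicide". SAP 14.6.3.2 plans two summaries from the clinician rating. The first is the worst post-Baseline rating, with a row for each category. The second is the number and percentage of subjects "reporting any post-OL Baseline rating of 3 or 4 will be tabulated". The denominator is tied to a given visit, although both summaries are overall ones.

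**Baseline.** Protocol 4.3, exclusion 7a, bars C-SSRS subjects who are actively suicidal, naming a yes to question 4 or 5, and those who have attempted suicide. 7b bars a GCAS score of 3 or 4. 7c bars active suicidality in the Investigator's judgment. SAP 8.2 tabulates suicidality at open-label Baseline on each scale.

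**The concern.** Three features make the planned output hard to read as a statement about the study's subjects.

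- A subject with open-label assessments on both scales belongs to both denominators, and one who is positive on both is counted in both numerators. The two tables cannot be added to give a per-subject proportion.
- The two yes/no counts put a wish to be dead on opposite sides of the line. Protocol 9.5.2 names them one after the other as the summary for each scale, so a reader is likely to set them side by side.
- A post-Baseline yes on the C-SSRS may be ideation that was already there at open-label Baseline. SAP 8.2 describes Baseline status and SAP 14.6.3.1 describes post-Baseline status, but nothing crosses the two.

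At stake is a simple descriptive figure: how many subjects had any suicidality on open-label drug, and in how many it was not there at the start.

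**Working it through.** The documents state no suicidality rate, no share of subjects on each scale and no switching rate, so there is no figure to reproduce. The check is a side-by-side reading, then arithmetic on assumed rates.

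**Step 1. Line up the definitions.**

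| State | C-SSRS (SAP 5.3.4, 14.6.3.1) | GCAS (SAP 5.3.5, 14.6.3.2) |
|---|---|---|
| Wish to be dead | Question 1: in the yes/no count | Rating 2: not in the 3-or-4 count, shown in the worst-rating table |
| Active suicidal thoughts, questions 2-5 | In the yes/no count | Approximately rating 3: in the count |
| Attempt | Behavior: in the count | Rating 4: in the count |
| Denominator | Subjects with an open-label C-SSRS | Subjects with an open-label GCAS at a given visit |

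**Step 2. Threshold effect, assuming the same true distribution on both scales.** Let P be the share whose worst state is a wish to be dead and A the share with anything worse (both assumed).

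- C-SSRS any suicidality = P + A
- GCAS 3 or 4 = A
- GCAS 2 to 4 = P + A

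With P = 3% and A = 1%, these are 4%, 1% and 4%. Over P = 1-5% and A = 0.5-2%, the ratio A/(P + A) runs from 0.5/5.5 = 0.09 to 2/3 = 0.67. Adding rows 2, 3 and 4 of the planned worst-rating table removes this gap.

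**Step 3. Adding the two yes/no counts.** Take N = 750 (the planned number), P = 3%, A = 1%, no switching.

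| On GCAS | C-SSRS count | GCAS 3-4 count | Sum | Aligned count |
|---|---|---|---|---|
| 20% | 600 × 0.04 = 24 | 150 × 0.01 = 1.5 | 25.5 | 750 × 0.04 = 30 |
| 50% | 375 × 0.04 = 15 | 375 × 0.01 = 3.75 | 18.75 | 30 |
| 80% | 150 × 0.04 = 6 | 600 × 0.01 = 6 | 12 | 30 |

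The sum moves with the scale mix alone.

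**Step 4. Switchers.** If a fraction s of 750 subjects has open-label assessments on both scales, the denominators sum to 750 × (1 + s): 787.5 at 5%, 825 at 10% and 900 at 20% (s assumed). Adding GCAS rows does not repair this.

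**Step 5. Baseline status.** A subject answering yes only to questions among 1-3 does not meet the question 4-5 criterion. The wider wording of 7a, and 7c, may exclude some of these subjects but need not exclude all. Those who enter and report unchanged ideation count as post-Baseline cases. For eligible subjects on the GCAS from Baseline, 7b has already removed ratings 3 and 4, so a later 3 or 4 is new relative to Baseline. The gap is therefore on the C-SSRS side, and among subjects who switch later.

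**Step 6. Look-back.** SAP 5.3.5 has the first GCAS cover lifetime and the past 3 months. For someone who switches during the study, the SAP does not say whether that rating enters the post-Baseline summary. If it does, history from before the study could be counted as on-treatment.

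**The case against.** A reader might infer that suicidality will look lower by definition in the more cognitively impaired subjects, because the GCAS goes to those who cannot complete the C-SSRS and its yes/no count starts higher. The documents do not support that, for four reasons.

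- The worst-rating table gives rating 2 its own row. Each subject has one worst rating, so a count of 2 or above follows by addition and a separate row for it would add nothing.
- GCAS 2, "2=wishes he/she were dead or any thoughts of possible death to self", is broader than C-SSRS question 1. The two are not the same state.
- The GCAS draws on caregiver report and clinician assessment as well as the subject, and a switcher's first GCAS looks back over a lifetime. Either could raise GCAS ratings.
- Allocation rests on the Investigator's judgment and on the scale used in the antecedent study, not on an MMSE cut-off alone.

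It is also fair to say that the 3-or-4 count matches Protocol 9.5.2 and exclusion 7b, so it is a consistent, prespecified definition and not an error. The study is descriptive ("No hypothesis testing is planned. Descriptive summaries of all safety and efficacy endpoints will be provided") and suicidality is exploratory. All data are listed, and suicidal events reported as adverse events enter per-subject tables on the Safety Analysis Set.

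All of this stands. It does not supply a scale-based count of each subject once, remove switchers from the double denominator, or cross post-Baseline C-SSRS ideation with Baseline.

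**Conclusion.** The point holds as a minor gap in presentation. Three things rest on the text alone: no once-per-subject table exists, switchers can sit in both denominators, and the C-SSRS post-Baseline count does not separate ideation already present at open-label Baseline. The threshold difference is real but limited. It misleads only if the two yes/no counts are compared or added, and the direction of any observed difference cannot be predicted.

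The size is illustrative. The 25.5, 18.75 and 12 against 30, and the denominators of about 788 to 900, depend on assumed rates, scale shares and switching, on equal true rates in both groups, and on treating GCAS 2 as matching C-SSRS question 1. Large fold differences between the two yes/no rates can be produced from such assumptions, but they should not be read as an expected result.

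A reader might also infer that the Baseline criteria admit everyone with ideation short of question 4. They do not: 7a and 7c reach further than that, and 7b already covers GCAS 3 and 4.

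**What to change.** Keep the planned per-scale tables and make these changes in SAP 14.6.3.

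1. **Add one supplementary table** over subjects with at least one post-Baseline open-label assessment on either scale, each counted once at the worst level. Nested tiers:
   - any: C-SSRS ideation or behavior, or GCAS 2 or above;
   - active ideas or behavior: C-SSRS questions 2-5 or behavior, or GCAS 3 or above;
   - attempt or suicide: C-SSRS actual attempt or suicide, or GCAS 4.
2. **Split each tier** by present or absent at open-label Baseline, and show it by scale and for switchers.
3. **State a look-back rule.** Leave the lifetime and past-3-month ratings of a switcher's first GCAS out of the post-Baseline count, or show them separately.
4. **Correct the denominator** of the overall GCAS counts from one tied to a visit to subjects with at least one post-Baseline open-label GCAS assessment.

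The cost is SAP wording and one table from data already collected. The downside is that the mapping between scales is approximate: GCAS 2 also takes in thoughts of one's own possible death and may capture some subjects who would answer yes to C-SSRS question 2. A footnote should say so.

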	
Adverse events leading to discontinuation, AEs related to study drug, AEs by maximum severity, SAEs, and SAEs related to study drug will be reported.
 
Exploratory Analyses
 
For the C-SSRS, the number and percentage of subjects with suicidal ideation or suicidal behavior during this study will be tabulated. For the GCAS, the number and percentage of subjects with a score of 3 or 4 during this study will also be tabulated.
 
Descriptive summary statistics for MMSE and ESRS-A observed values and change from Baseline will be provided by timepoint.
 
Descriptive summary statistics for CGI-S, EQ-5D-5L, and SDI observed values and change from Baseline will also be provided by timepoint.
 
Other Safety Analyses
 
Descriptive summary statistics for ECG, vital signs and body weight, and clinical laboratory parameters, including observed values and changes from Baseline, will be tabulated by timepoint. Additionally, categorical analyses will be conducted on the incidence of subjects with prolonged QTc intervals and changes in QTc intervals in accordance with International Council for Harmonisation (ICH) guidelines.

Date	5 March 2021

Figure S-1 Schematic of Study Design for ACP-103-047

* Eligible subjects will begin pimavanserin dosing at 34 mg. Dose adjustments of pimavanserin down to 20 mg and up to 34 mg are permitted at any study visit (scheduled or unscheduled) after Baseline based on Investigator assessment of clinical response.

Table S–1 Schedule of Assessments for ACP-103-047

Visit Number	Baseline ^b	Treatment Period								Unscheduled Visit	Safety Follow-Up ^k
	1	2	3	4	5	6	7	8	(EOT/ET) 9		10
Visit Week ^a	Week 0	Week 2	Week 4	Week 8	Week 12	Week 16	Week 28	Week 40	Week 52		Week 56
Type of visit	Clinic	Clinic	Clinic	Clinic	Clinic	Clinic	Clinic	Clinic	Clinic	Clinic	Phone call
Allowable visit window (# days)		±3	±3	±3	±3	±7	±7	±7	±7		+4
Informed consent ^b	X										
Inclusion/exclusion criteria	X										
Medical history and demographics	X										
Psychiatric, dementia, and neurological history	X										
Physical examination	X						X		X		
Vital signs	X	X	X	X	X	X	X	X	X	X	
Weight	X	X	X	X	X	X	X	X	X		
ECG ^c	X	X	X	X	X	X	X	X	X		
Clinical laboratory tests	X				X				X		
Pregnancy test ^d	X	X	X	X	X	X	X	X	X		
Urine drug screen	X				X				X		
MMSE	X	X	X	X	X	X	X	X	X		
ESRS-A	X	X	X	X	X	X	X	X	X	X	
C-SSRS ^e or GCAS ^e	X	X	X	X	X	X	X	X	X	X	
CGI-S	X	X	X	X	X	X	X	X	X	X	
EQ-5D-5L	X				X		X		X		

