6.3.5.2 Global Clinician Assessment of Suicidality

The GCAS is a clinician-rated, 5-point scale that is designed to rate the subject's suicidality based on the report of the subject, the report of the study partner/caregiver, and the clinician's global assessment. Ratings can be 0 ("Absent"), 1 ("Feels life is not worth living"), 2 ("Wishes he/she were dead or any thoughts of possible death to self"), 3 ("Suicidal ideas or gesture"), or 4 ("Attempt at suicide"). The Investigator will record a subject rating, a study partner/caregiver rating, and a clinician rating.

If the GCAS was used in the antecedent study, suicidality since-last-visit will be assessed at Visit 1 (Baseline) and at all other visits.

If the subject is not able to reliably complete the C-SSRS at any point in the study in the Investigator's judgment, the GCAS will be administered and used thereafter in the study. The first assessment with the GCAS should assess lifetime suicidality and suicidality for the past 3 months and at all other visits, suicidality since the previous visit will be assessed.

As with the C-SSRS, if at any time the GCAS results for a given subject reveal potential suicidality, then the Investigator should assess the clinical significance of such results. If a clinically significant risk of suicidality is identified for a subject, then the Investigator should discontinue the subject and implement appropriate treatment ([Section 4.4](#)).

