9.5.2 Exploratory Analyses

For the C-SSRS, the number and percentage of subjects with suicidal ideation or suicidal behavior during the study will be tabulated. For the GCAS, the number and percentage of subjects with a score of 3 or 4 during the study will be tabulated. The number and percentage of subjects for each GCAS rating (0-4) will also be tabulated by timepoint and informant (subject, study partner/caregiver, and clinician).

Descriptive summary statistics for MMSE and ESRS-A observed values and change from Baseline will be provided by timepoint.

Descriptive summary statistics for CGI-S, EQ-5D-5L, and SDI observed values and change from Baseline will also be provided by timepoint.

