8.2 Disease Characteristics and Neuropsychiatric History

Disease characteristics at OL Baseline will be summarized using descriptive statistics. MMSE total score, CGI-S, EQ-5D-5L VAS, SDI total score, and ESRS-A total score will be presented as continuous variables. In addition, CGI-S will be presented as a categorical

variable using categories of 1 to 7, and MMSE will be presented as a categorical variable using categories of ≤ 10 , 11 to 17, 18 to 24, and 25 to 30. For the C-SSRS the number and percentage of subjects having suicidal ideation or behavior since the last visit will be presented. For the GCAS, the number and percentage of subjects within each rating since the last visit (absent, feels life is not worth living, wishes he/she were dead or any thoughts of possible death to self, suicidal ideas or gestures, and attempts at suicide) will be presented.

Neuropsychiatric history will be summarized descriptively for continuous and categorical variables. The OL Baseline visit date will be used as the reference date for calculation of durations. For both the Disease Characteristics and Neuropsychiatric History, summaries by region (North America, Europe, and rest of world) will also be presented. The Neuropsychiatric history will be pushed into the -047 database from the -046 study. If there have been any changes in the subject's neuropsychiatric history since completing this form for the -046 study, appropriate updates should be made by editing the affected fields.

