19 CHANGES TO ANALYSES SPECIFIED IN PROTOCOL

None.

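### SAP 14.6.3.2 leaves out the protocol's GCAS table by timepoint and informant without declaring it, and gives two across-visit summaries a per-visit denominator

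*SAP*

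**What the plan says.** **Collection.** Protocol 6.3.5.2 provides for three ratings at each GCAS assessment: "The Investigator will record a subject rating, a study partner/caregiver rating, and a clinician rating". SAP 5.3.5 repeats this.

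**Protocol analysis.** Protocol 9.5.2 asks for a count of subjects scoring 3 or 4. It then adds a second table, in which "each GCAS rating (0-4) will also be tabulated by timepoint and informant (subject, study partner/caregiver, and clinician". The synopsis is shorter and gives only the first item: "For the GCAS, the number and percentage of subjects with a score of 3 or 4 during this study will also be tabulated".

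**SAP analysis.** SAP 14.6.3.2 plans two post-Baseline summaries, the overall worst rating and any rating of 3 or 4. Both are for the OL period and use clinician ratings. On the other two informants it says: "Subject and study partner/caregiver ratings will not be summarized but will be included in data listings". For percentages in these summaries, "the denominator is the number of subjects with an OL GCAS assessment at the given visit and within each cohort".

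**Elsewhere in the SAP.** Section 8.2 has one distribution at OL Baseline: "For the GCAS, the number and percentage of subjects within each rating since the last visit". It names no informant. For the C-SSRS, Section 14.6.3.1 says that "the denominator will be the number of subjects with an OL C-SSRS assessment within each cohort". Section 19, headed "CHANGES TO ANALYSES SPECIFIED IN PROTOCOL", consists of the one word None.

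**The concern.** There are two separate defects.

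First, a safety table that the protocol body promises is missing from the SAP, and the section meant to record such departures says that there are none. Suicidality is a named exploratory safety objective, and the GCAS is the instrument for subjects who cannot reliably complete the C-SSRS. Under the SAP, a subject whose own or caregiver rating is 3 or 4, but whose clinician rating is lower, would appear in no post-Baseline GCAS summary, only in a listing. The course of ratings over the 52 weeks would not be tabulated for any informant.

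Second, the two summaries that remain carry a denominator that does not belong to them. A worst rating over all visits, or any 3 or 4 over all visits, is a statement about a subject, not about a visit. A programmer has no stated visit to use, and different choices would give different percentages for the same count.

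**Working it through.** The plan gives no GCAS count or rate, so there is no figure to reproduce. The check sets the texts side by side, with a little algebra.

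**1. Is it the same protocol version?** SAP Section 1 says that it elaborates protocol amendment 4 of 05 March 2021. The protocol synopsis carries that date. The difference is not explained by a later protocol.

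**2. Table required against table planned.**

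| Item | Protocol 9.5.2 | SAP |
|---|---|---|
| Any rating of 3 or 4 | Yes | Yes, clinician (14.6.3.2) |
| Overall worst rating | Not requested | Yes, clinician (14.6.3.2) |
| Ratings 0 to 4 by timepoint, clinician | Yes | No post-Baseline table |
| Ratings 0 to 4 by timepoint, subject | Yes | Listed only |
| Ratings 0 to 4 by timepoint, caregiver | Yes | Listed only |
| Ratings at OL Baseline | Within the above | Yes, informant not stated (8.2) |

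Scheduled post-Baseline visits are Weeks 2, 4, 8, 12, 16, 28, 40 and 52, which is 8. Distributions required after Baseline: 8 visits × 3 informants = 24. Planned: 0. This describes the content of one table, not 24 separate failures.

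**3. The denominator.** For one cohort, let A be the number of subjects with at least one post-OL Baseline GCAS assessment. Let a_k be the number whose worst rating is k (k = 0 to 4), so the a_k sum to A. Let N_v be the number assessed at post-Baseline visit v, so N_v ≤ A.

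- Per-subject rule: 100 × a_k / A. The five categories sum to 100 × A / A = 100%.
- Rule as written, if one visit v is used: 100 × a_k / N_v. The categories sum to 100 × A / N_v, which exceeds 100% whenever N_v < A. The any-3-or-4 percentage is raised by the same factor, A / N_v.

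There are 8 candidate values of N_v, and the SAP names none of them. Missed visits, early withdrawals and subjects who move to the GCAS part-way through all make N_v smaller than A. The gap can also be related to outcome. Protocol 6.3.5.2 tells the Investigator to discontinue a subject with clinically significant suicidality risk, and that subject then stays in the numerator but leaves later visits' denominators. The documents do not give A or any N_v, so no size follows.

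**4. The SAP's own convention.** For overall post-Baseline summaries of laboratory, vital sign and ECG values (14.2.5.3, 14.3.2 and 14.4.2.2), the denominator is subjects having at least one post-Baseline measurement. The C-SSRS rule has no visit term. The GCAS rule is the exception.

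**5. Minor note: look-back ratings.** Protocol 6.3.5.2 and SAP 5.3.5 have the first GCAS after a switch from the C-SSRS cover lifetime and the past 3 months. Three months by the conversion in SAP 5.1 is 3/12 × 365.25 = 91.3 days. The first dose is on the day after Baseline, so days from first dose to visit = days from Baseline ± visit window − 1.

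| Switch visit | Days after first OL dose | Recall before first dose (91.3 − days) |
|---|---|---|
| Week 2 | 14 ± 3 − 1 = 10 to 16 | 75.3 to 81.3 |
| Week 4 | 28 ± 3 − 1 = 24 to 30 | 61.3 to 67.3 |
| Week 8 | 56 ± 3 − 1 = 52 to 58 | 33.3 to 39.3 |
| Week 12 | 84 ± 3 − 1 = 80 to 86 | 5.3 to 11.3 |
| Week 16 | 112 ± 7 − 1 = 104 to 118 | none |

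At in-window visits from Week 16 on, the past-3-month rating lies wholly after the first OL dose. A lifetime rating always reaches back before it. These are window lengths, not misclassification rates.

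**The case against.** **The omission is open and small.** SAP 14.6.3.2 says plainly that two informants will only be listed. The GCAS is a clinician-rated scale that draws on subject and caregiver report, so the retained rating already reflects both. The synopsis asks only for the 3-or-4 count, which is kept. Nothing is tested and every rating is listed. All of this stands, and it limits the weight of the point. It does not remove it: the protocol body makes a firm commitment to the table, the shorter synopsis does not cancel it, and Section 19 is inaccurate while it says None. Table specifications sit in a separate document, but they could not restore the subject and caregiver summaries without contradicting the SAP.

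**The denominator is a drafting slip that quality control would catch.** This is plausible. Worst-rating categories summing to more than 100% would be noticed, and the neighbouring rules show what was probably meant. The any-3-or-4 percentage has no such visible check, though, and a rule that has to be guessed at should be corrected in the text.

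**Stronger readings that a reader might infer.** One is that the percentages will be inflated by some stated factor. The documents give no GCAS numbers by visit and do not say that a single visit will be used, so no factor can be supported. Another is that pre-dose history of subjects who switch scales will be reported as on-study suicidality. The documents do not establish that either. They do not describe how look-back ratings are stored or how many subjects switch. SAP 5.4.2 refers to a separate programming conventions document, and exclusion criterion 7 limits recent pre-dose events. Nor would it be sound to take undatable early ratings out of the main count. SAP 5.5.3 treats an adverse event of unclear timing as treatment-emergent, and removing such ratings could hide a rating of 1 or 2 altogether.

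**Conclusion.** Both parts hold on the text. The SAP omits a GCAS table that Protocol 9.5.2 requires (0 of 24 post-Baseline distributions planned) and declares no change. The denominator for its two remaining GCAS summaries cannot be applied as written and departs from the SAP's own convention. If a single post-Baseline visit not attended by all were used, the error would be upward; its size cannot be estimated from the documents.

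This should be corrected, but it is of moderate weight. The analyses are exploratory and descriptive, the clinician 3-or-4 count survives and the listings are complete. The documents do not support reading the omission as a loss of the GCAS safety signal, or as a deliberate withholding of it. The look-back question is a minor matter of clarity.

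**What to change.** In SAP 14.6.3.2:

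- **(a)** Restore the table of ratings 0 to 4 by timepoint and informant and attach the per-visit denominator to it. Alternatively, record the removal in Section 19 with a justification.
- **(b)** For the overall worst rating and the any-3-or-4 count, use as denominator the subjects in each cohort with at least one post-OL Baseline GCAS assessment.
- **Minor clarification.** Keep all post-OL Baseline ratings in the main count, exclude only those recorded as lifetime ratings, and footnote past-3-month ratings from switch visits whose recall window reaches before the first OL dose (in-window Weeks 2 to 12).

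The cost is SAP wording and one restored table, or one Section 19 entry in its place, plus a footnote. All three ratings are already collected, and no study procedure changes.
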